5.2.10. Idelalisib Dose Adjustments

The dose adjustment recommendations and requirements in [Table 5-2](#) are based on the Common Terminology Criteria for Adverse Events (CTCAE) grade of specific toxicities. However, exceptions are expected for subjects who initiate study treatment with low blood counts. Clinical judgment should apply, and in cases of uncertainty, the study medical monitor should be contacted.

The dose modification instructions in [Table 5-2](#) focus on the types of events most commonly associated with idelalisib. The modifications include both recommended and required actions. When a modification is indicated as a recommendation, it serves as a guideline; variations from the recommendation may be warranted based on an investigator's individual judgment in considering potential risks, benefits, and therapeutic alternatives available to each subject.

Table 5-2. Dose Adjustment Guidelines {Gilead Sciences Inc 2014}

NCI CTCAE Grade ^a	Idelalisib
HEMATOLOGICAL ADVERSE EVENTS	
Neutropenia	
Grade \leq 2 neutropenia	Recommended Action: Maintain current dose level and schedule.
Grade \leq 3 neutropenia	Required Action: Monitor blood counts at least weekly until ANC \leq Grade 2. Recommended Action: Maintain current dose level and schedule.
Grade 4 neutropenia (or occurrence of neutropenic fever or infection)	Required Action: 
Withhold idelalisib.Monitor blood counts at least weekly until ANC \leq Grade 2 Recommended Action: 
May resume idelalisib at lower dose level when ANC grade is \leq Grade 3Neutropenia should be managed according to established clinical guidelines.
Thrombocytopenia	
Grade \leq 3	Recommended Action: Maintain current dose level and schedule.
Grade 4	Required Action: Withhold idelalisib for bruising or bleeding until Grade \leq 3. Recommended Action: May resume idelalisib at initial or reduced dose level at investigator discretion.
NON-HEMATOLOGICAL ADVERSE EVENT	
Rash	
Grade \leq 1	Recommended Action: Maintain current dose level and schedule
Grade 2	Recommended Action: Maintain current dose level and schedule
Grade \geq 3	Required Action: Withhold idelalisib until Grade \leq 1. Recommended Action: Resume at lower dose level or discontinue idelalisib at investigator discretion.
Stevens-Johnson Syndrome (SJS)/Toxic Epidermal Necrolysis (TEN)	
Any Grade	Required Action: 
Discontinue idelalisib.Institute treatment per institutional standards.Interrupt co-administered medications potentially associated with SJS/TEN.
Bowel Perforation	
Any Grade	Required Action: Discontinue idelalisib

NCI CTCAE Grade ^a	Idelalisib
Gastrointestinal Inflammation/Diarrhea^b	
Grade ≤1	
Required Action:
 
• Obtain history of onset and duration of diarrhea, including description, number of stools, stool composition (e.g., watery, bloody, nocturnal), travel history, dietary changes and a medication review to identify possible diarrheogenic agents.• Perform physical examination including assessment for fever, dizziness, abdominal pain/cramping, and weakness (e.g., evaluate for sepsis, bowel obstruction, dehydration). 
Recommended Action: Provide anti-diarrheal agent (eg, loperamide) and maintain current idelalisib dose level and schedule

Grade ≥ 2 diarrhea or colitis (unless clinical diagnosis is established from medical history and physical examination)	
Required Action:
 
• Obtain history of onset and duration of diarrhea, including description of number of stools and stool composition (e.g., watery, bloody, nocturnal), travel history, dietary changes and a medication review to identify possible diarrheogenic agents.• Perform physical examination including assessment for fever, dizziness, abdominal pain/cramping, and weakness (e.g., evaluate for sepsis, bowel obstruction, dehydration).• For Grade 2 colitis or diarrhea (unless clinical diagnosis is established from medical history and physical examination), perform stool culture for routine pathogens (Salmonella, Shigella, Campylobacter species, test for Clostridium difficile toxin, Rotavirus, Cytomegalovirus (CMV), Adenovirus), ova and parasites (Cryptosporidium parvum, Isospora belli, Enterocytozoon bieneusi, Septata intestinalis, Strongyloides, Microsporidia, Entamoeba histolytica, Cyclospora), and Giardia antigen. 
Recommended Action: Provide anti-diarrheal agent (eg, loperamide) and maintain current idelalisib dose level and schedule

Grade ≥ 3 diarrhea or colitis or persistent Grade 2 diarrhea or colitis without clear etiology	
Required Action:
 
• Dosing: Withhold idelalisib• Consider anti-diarrheal (eg, loperamide) and/or addition of anti-inflammatory agent (eg, sulfasalazine, budesonide).• Obtain history of onset and duration of diarrhea, including description, number of stools, stool composition (e.g., watery, bloody, nocturnal), travel history, dietary changes and a medication review to identify possible diarrheogenic agents.• Perform physical examination including assessment for fever, dizziness, abdominal pain/cramping, and weakness (e.g., evaluate for sepsis, bowel obstruction, dehydration).• For Grade 3 colitis or diarrhea (unless clinical diagnosis is established from medical history and physical examination), perform stool culture for routine pathogens (Salmonella, Shigella, Campylobacter species, testing for Clostridium difficile toxin, Rotavirus, Cytomegalovirus (CMV), Adenovirus), ova and parasites (Cryptosporidium parvum, Isospora belli, Enterocytozoon bieneusi, Septata intestinalis, Strongyloides, Microsporidia, Entamoeba histolytica, Cyclospora), and Giardia antigen.

NCI CTCAE Grade ^a	Idelalisib
	
Recommended Action:
 
• Dosing: At Grade ≤ 1, may resume at lower dose level or discontinue idelalisib at investigator discretion.• Endoscopy with biopsy is strongly recommended to assess by immunohistochemistry (IHC) and PCR for CMV, Adenovirus PPD• Provide anti-diarrheal agent (eg, loperamide) and maintain current idelalisib dose level and schedule
Hepatic Adverse Events (elevations in ALT, AST, or bilirubin)	
Grade ≤ 1 (ALT/AST $\leq 3\times$ ULN) (Bilirubin $\leq 1.5\times$ ULN)	Recommended Action: Maintain current dose level and schedule.
Grade 2 (ALT/AST $> 3\text{-}5\times$ ULN) (Bilirubin $> 1.5\text{-}3\times$ ULN)	
Recommended Action: Maintain current dose level and schedule
 
Recommended Action: Monitor ALT, AST, ALP, and bilirubin at least 1x per week until all abnormalities are Grade ≤ 1; thereafter, maintain current dose level.

Grade 3 (ALT/AST $> 5\text{-}20\times$ ULN) (Bilirubin $> 3\text{-}10\times$ ULN)	
Recommended Action: Withhold idelalisib.
 
Required Action:
 
• Monitor ALT, AST, ALP, and bilirubin at least 1x per week until all abnormalities are Grade ≤ 1.• If bilirubin abnormality is Grade < 3, resume idelalisib at same dose level. If bilirubin abnormality is Grade ≥ 3, resume at lower dose level.
Grade 4 (ALT/AST $> 20\times$ ULN) (Bilirubin $> 10\times$ ULN)	
Required Action:
 
• Withhold idelalisib.• Monitor ALT, AST, ALP, and bilirubin at least 1x per week until all abnormalities are Grade ≤ 1.• If bilirubin abnormality is Grade 4, discontinue idelalisib. 
Recommended Action: If bilirubin abnormality is Grade < 4, resume study drug at lower dose level.

Pneumonitis (dyspnea, cough, hypoxia without obvious infectious cause)	
Grade ≤ 1	Recommended Action: Withhold idelalisib until resolution to baseline. May resume at lower dose level or discontinue idelalisib at investigator discretion.
Grade ≥ 2	
Required Action:
 
• Discontinue idelalisib. 
Recommended Action:
 
• Consider bronchoscopy to evaluate for PJP, CMV and other organisms (bacterial and viral)• Consider treatment with systemic corticosteroids.• Consider empiric treatment of pneumocystis if bronchoscopy is contraindicated• Upon resolution, may resume idelalisib at lower dose level at investigator discretion and /Gilead medical monitor agreement

NCI CTCAE Grade ^a	Idelalisib
Pneumocystis jirovecii pneumonia (PJP)	
Any Grade	Required Action: Discontinue idelalisib
Uequivocal CMV infection^c	
Any Grade	Required Action: 
Interrupt idelalisib upon unequivocal clinical or laboratory evidence of CMV infection.Treat according to established clinical guidelines.If the benefits of resuming idelalisib are judged to outweigh the risks, consideration should be given to administering pre-emptive CMV therapy.
Other Nonhematological Adverse Events	
Grade ≤ 2	Recommended Action: Maintain current dose level and schedule
Grade ≥ 3	Recommended Action: Withhold idelalisib until Grade ≤ 1 . May resume idelalisib at initial or lower dose level or discontinue idelalisib at investigator discretion.

a CTCAE, Version 4.03.

b See section [6.2](#) and [7.3.2](#) for additional requirements regarding an AE of diarrhea

c CMV should be diagnosed using clinical or laboratory criteria per established institutional standard

Abbreviations: ALP=alkaline phosphatase, ALT=alanine aminotransferase, ANC=absolute neutrophil count, AST=aspartate aminotransferase, CTCAE=Common Terminology Criteria for Adverse Events, CMV=cytomegalovirus, G-CSF=granulocyte-colony-stimulating factor, NCI=National Cancer Institute, ULN=upper limit of normal

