6.2.2.1. Evaluation for Gastrointestinal Events/Colitis

For Grade 2 colitis and diarrhea (unless clinical diagnosis is established from medical history and physical examination), the following testing is required:

- Stool culture for routine pathogens (Salmonella, Shigella, Campylobacter species, Clostridium difficile toxin, Rotavirus, Cytomegalovirus, Adenovirus)
- Stool for Ova and Parasites (Cryptosporidium parvum, Isospora belli, Enterocytozoon bieneusi, Septata intestinalis, Strongyloides, Microsporidia, Entamoeba histolytica, Cyclospora), Giardia antigen

For Grade ≥ 3 or persistent Grade 2 colitis or diarrhea without clear etiology (eg, clostridium difficile enterocolitis), endoscopy with biopsy is strongly recommended. All biopsy samples should include immunohistochemistry (IHC) and PCR for CMV, Adenovirus.

PPD

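### Table 5-2 recommends maintaining the idelalisib dose in the same diarrhea/colitis row that requires withholding it, and the row above has no upper grade limit

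*Protocol*

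**What the plan says.** Table 5-2 has three rows for gastrointestinal inflammation and diarrhea: Grade 1 or lower; a row headed "Grade ≥ 2 diarrhea or colitis (unless clinical diagnosis is established from medical history and physical examination" (the heading then closes its parenthesis); and a row for Grade 3 or higher, or persistent Grade 2 without clear etiology, called the severe row below.

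The severe row makes three statements about dosing:

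- Required: "Dosing: Withhold idelalisib".
- Recommended, first bullet: "Dosing: At Grade ≤ 1, may resume at lower dose level or discontinue idelalisib at investigator discretion".
- Recommended, last bullet: "Provide anti-diarrheal agent (eg, loperamide) and maintain current idelalisib dose level and schedule".

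The last of these is word for word the recommended action of both lower-grade rows.

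The stool-test bullets also differ by row. The middle row has "For Grade 2 colitis or diarrhea (unless clinical diagnosis is established from medical history and physical examination), perform stool culture for routine pathogens"; the severe row has "For Grade 3 colitis or diarrhea (unless clinical diagnosis is established from medical history and physical examination), perform stool culture for routine pathogens". Section 6.2.2.1 has one paragraph beginning "For Grade 2 colitis and diarrhea (unless clinical diagnosis is established from medical history and physical examination), the following testing is required" and a separate one, on endoscopy, beginning "For Grade ≥ 3 or persistent Grade 2 colitis or diarrhea without clear etiology".

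The text of Section 5.2.10 says that the table contains both required and recommended actions, that a recommendation is a guideline from which the investigator may depart, and that uncertain cases go to the medical monitor.

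**The concern.** A drug cannot be withheld and also kept at its current dose and schedule. The severe row says both, for a toxicity that the protocol treats as serious. Section 7.3.2.1 reports that severe idelalisib diarrhea responds poorly to antimotility agents. It gives a median time to resolution of between 1 week and 1 month across trials after idelalisib was interrupted, with corticosteroids started in some instances. The stray bullet thus pairs continued dosing with the class of drug that the protocol says works poorly in severe cases.

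The middle row adds a second route to the same advice. Its heading starts at Grade 2 and has no ceiling, and the row contains no instruction to hold the drug. A site that stops at the first row matching a Grade 3 event may not reach the required hold.

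Sections 1.4 and 7.5.2 send the reader to Table 5-2 for toxicity management, so the wording of the table is what a site will act on.

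**Working it through.** There is no figure to reproduce, so the check compares texts.

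**Step 1: the three rows side by side.**

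| Row heading | Required dosing action | Recommended dosing action | Grade named in stool-test bullet |
|---|---|---|---|
| Grade 1 or lower | none | maintain | no such bullet |
| Grade 2 or higher, unless a clinical diagnosis is established | none | maintain | Grade 2 |
| Grade 3 or higher, or persistent Grade 2 without clear etiology | withhold | (i) at Grade 1 or lower, resume lower or discontinue; (ii) maintain | Grade 3 |

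**Step 2: inside the severe row.** There are 3 dosing statements. Statement (ii) conflicts with the other 2: it contradicts the hold directly, and it contradicts the advice on leaving the hold because that advice names a lower level or discontinuation.

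**Step 3: can (ii) be read as advice for the period after resumption?** No. The row's advice on resuming is to go to a lower level, so the dose current at the time of the event is not kept. A subject who has recovered enough to resume is also at Grade 1 or lower, where the first row already gives the maintain recommendation. Nothing in the bullet limits it to that period.

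**Step 4: which events fall in two rows?** The middle heading excludes events with a clinical diagnosis established from history and examination.

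| Event | Rows met | Required withhold | Recommended maintain |
|---|---|---|---|
| Grade 3-4, no established clinical diagnosis | middle and severe | 1 | 2 |
| Persistent Grade 2 without clear etiology, no established clinical diagnosis | middle and severe | 1 | 2 |
| Grade 3-4, clinical diagnosis established | severe only | 1 | 1 |

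These are counts of conflicting text, not measures of risk. The Step 2 conflict is present in every line; the heading overlap affects only the first two.

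**Step 5: what split was intended?** Section 6.2.2.1 treats Grade 2 apart from Grade 3 or higher and persistent Grade 2. The stool-test bullets point the same way: the middle row's names Grade 2 and the severe row's names Grade 3. A middle row confined to Grade 2 fits both.

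**Step 6: does another place correct the table?** Footnote b of the table points to Sections 6.2 and 7.3.2. Section 6.2 adds history and examination steps. Section 7.3.2 requires discontinuation for bowel perforation and says that subjects with enteritis have been able to stay on or go back to idelalisib, without naming a grade. Section 7.3.2.1 supports interruption. None of these removes the stray bullet.

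**Step 7: is it an artifact of the text?** No. The blacked-out text is in the neighboring endoscopy bullet, and the maintain bullet is complete.

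**The case against.** The strongest reply is that the protocol ranks its own instructions. Withholding is required and maintaining is only recommended; a recommendation is a guideline, and doubtful cases go to the medical monitor. A careful site would withhold. On this view the bullet is an editorial slip. This stands as a limit on the practical risk. It does not make the row consistent, and a dosing table for a known serious toxicity should not rely on the reader to override part of it.

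On the heading, two replies have force. A reader might infer that every Grade 3-4 event falls in both rows. The documents do not support that, because the middle heading excludes events with an established clinical diagnosis. Many readers would also turn to the more specific, higher-grade row, which holds the required action. Overlapping headings occur elsewhere in the table too: the first two neutropenia rows overlap, but both recommend maintaining the dose, so no conflict arises there. The heading is therefore a secondary defect.

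The stool-test bullets are loosely drafted themselves. The severe row's bullet names neither Grade 4 nor persistent Grade 2, both of which its heading covers. They are weak evidence of intent, and Section 6.2.2.1 is the better support.

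Section 7.3.2 could be cited in favor of maintaining the dose, since it mentions subjects who continued idelalisib. It gives no grade, so it cannot justify that recommendation in a row that requires a hold.

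**Conclusion.** The contradiction in the severe row is real and should be fixed: 1 of its 3 dosing statements conflicts with the other 2. The open-ended Grade 2 heading is a lesser defect, confined to Grade 3-4 and persistent Grade 2 events without an established clinical diagnosis.

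A reader might infer that the protocol tells sites to dose through severe colitis, or that subjects were harmed or results distorted. The documents support none of these. The binding instruction is to withhold. SAP Section 1.3 reports 3 subjects enrolled, and the SAP plans listings without hypothesis tests or efficacy analyses, so no analysis turns on this wording.

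The conclusion assumes that the words on unclear etiology in the severe row's heading qualify persistent Grade 2 only. If they also qualify Grade 3 or higher, fewer events enter that row but the conflict inside it is unchanged. That the bullet was carried down from the lower-grade rows is an inference from identical wording. The documents do not say whether any subject is still on treatment, which decides whether the correction affects care or only the record.

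**What to change.** 1. In the severe row, delete the last recommended bullet. At the least, delete its second half, on maintaining the dose level and schedule. Nothing is lost by removing it all, because the row's required list already says to consider an anti-diarrheal.
2. Re-head the middle row as Grade 2 diarrhea or colitis, other than persistent Grade 2 without clear etiology, and keep the existing exception for an established clinical diagnosis.
3. In the severe row's stool-test bullet, change Grade 3 to Grade 3 or higher or persistent Grade 2. Item 2 should not be made without this. Otherwise persistent Grade 2 would move into a row whose stool tests name only Grade 3, while Section 6.2.2.1 still requires them for Grade 2. The change also brings in Grade 4.

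The cost is a clarification letter or a protocol wording amendment. No new data, visits or subjects are needed, and the SAP does not change.

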7.3.3. Hepatic Events

Transaminase Elevations: Consistent with observations in a dog toxicology study, reversible asymptomatic ALT/AST increases were also observed early in the idelalisib program in phase 1 studies (101-02 and 101-07) in subjects with hematologic malignancies. Transaminase elevations generally occurred within 4 to 12 weeks of drug initiation, and resolved spontaneously over a period of 2 to 4 weeks with drug being continued for Grade 1 and 2 elevations and drug withheld for Grade 3 or 4 elevations until resolution. These early observations have been consistent with the ongoing experience with idelalisib treatment and transaminase elevations are now well characterized as most frequently asymptomatic, transient and occurring within the first 3 months of treatment.

Grade 1 or 2 elevations commonly resolve despite continued idelalisib treatment and Grade 3 or 4 elevations can be managed by withholding idelalisib. Successful rechallenge after resolution at either the same or lower dose level of idelalisib has been achieved in the majority of subjects. There has been no evidence of impaired synthetic function. Close monitoring of hepatic laboratory tests during therapy is important to allow for appropriate idelalisib interruption and reinstitution so that subjects may continue with study drug treatment.

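### The Grade 3 hepatic row of Table 5-2 makes withholding advisory and restart mandatory, and its restart instruction states no recovery condition

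*Protocol*

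**What the plan says.** Protocol Table 5-2 (Section 5.2.10) sorts its instructions into Required and Recommended Actions. Section 5.2.10 gives the labels their force: "When a modification is indicated as a recommendation, it serves as a guideline", and the investigator may depart from it on individual judgment.

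In the Grade 3 hepatic row:

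- The hold is advisory: "Recommended Action: Withhold idelalisib".
- Weekly liver tests are required "until all abnormalities are Grade ≤ 1".
- Also under Required Action: "If bilirubin abnormality is Grade < 3, resume idelalisib at same dose level" and "If bilirubin abnormality is Grade ≥ 3, resume at lower dose level".

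In the Grade 4 hepatic row, withholding is a Required Action and bilirubin of Grade 4 requires discontinuation. Restart is advisory: "Recommended Action: If bilirubin abnormality is Grade < 4, resume study drug at lower dose level".

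Three other sections bear on the row:

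- **Section 5.2.9** allows a hold for an event suspected to be related to idelalisib until it has resolved or stabilised acceptably, with the acceptable degree left to Table 5-2. After that, idelalisib may be restarted.
- **Section 5.5** lets the investigator stop idelalisib in the subject's interest, and says that study drug should stop when benefit-risk is not judged positive.
- **Section 7.3.3**, on transaminase elevations in phase 1 studies, reports "drug withheld for Grade 3 or 4 elevations until resolution" and describes rechallenge as coming after resolution.

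**The concern.** The labels decide what an investigator must do and what may be varied. In this row they bind the restart and leave the hold open, and the restart has no stated starting point. Following the table exactly, an investigator may dose through a Grade 3 hepatic event without departing from anything required. One who holds and then prefers not to restart departs from a Required Action.

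This matters because Section 1.4 bases its positive benefit/risk conclusion partly on toxicity management as set out in Table 5-2. The SAP also gives liver abnormalities their own listing (Section 7.2.2) and lists important protocol deviations (Section 4.3), so it should be clear which conduct departs from the protocol.

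**Working it through.** No sample size, error rate or event count bears on this point, so the check is a comparison of texts.

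**Step 1. Labels on hold and restart across Table 5-2.** These are the rows that pair a temporary hold with a graded or baseline-based restart.

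| Row | Hold | Restart | Recovery level tied to hold or restart |
|---|---|---|---|
| Neutropenia, Grade 4 | Required | Recommended | Grade ≤ 3 |
| Thrombocytopenia, Grade 4 | Required (bruising or bleeding) | Recommended | Grade ≤ 3 |
| Rash, Grade ≥ 3 | Required | Recommended | Grade ≤ 1 |
| Diarrhea/colitis, Grade ≥ 3 or persistent Grade 2 | Required | Recommended | Grade ≤ 1 |
| **Hepatic, Grade 3** | **Recommended** | **Required** | **None stated** |
| Hepatic, Grade 4 | Required | Recommended | None stated |
| Pneumonitis, Grade ≤ 1 | Recommended | Recommended | Baseline |
| Other nonhematological, Grade ≥ 3 | Recommended | Recommended | Grade ≤ 1 |

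Grade 3 hepatic is the only one of the eight in which restart is required. The nearest case outside the list is CMV infection, where the text on resuming also stands under Required Action but depends on a judgment that benefits outweigh risks. The two hepatic rows are the only ones of the eight with no recovery level tied to the hold or restart.

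**Step 2. Does Section 5.2.9 supply the missing condition?** It orders events as hold, then recovery, then restart, but sends the reader to Table 5-2 for the degree of recovery. The only level in the Grade 3 hepatic row is Grade ≤ 1, attached to the end of weekly monitoring. The reference therefore does not close the gap. Section 5.2.9 also makes restart permissive, while the row makes it required.

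**Step 3. What can the bilirubin grade mean?** Two things are unstated: whether the grade is current or worst, and whether restart waits for Grade ≤ 1.

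| Bilirubin grade | Restart waits for Grade ≤ 1 | Restart does not wait |
|---|---|---|
| Current | At restart bilirubin is already Grade ≤ 1, so the Grade ≥ 3 instruction can never apply | The Grade ≥ 3 instruction calls for dosing while bilirubin is still Grade ≥ 3, against the row's own advice to withhold |
| Worst in the event | Both instructions work: one for transaminase-only events, one for events with Grade 3 bilirubin | The dose level is fixed but the time of restart is not |

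Only one of the four readings is complete, and it needs two elements that the row does not state.

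**Step 4. What if the hold is not applied?** The row allows this, but then there is nothing to resume. The row does not say whether the lower dose level still applies after Grade 3 bilirubin.

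**Step 5. Compliance as labelled.** Not holding: within Section 5.2.10. Holding and then restarting: compliant. Holding and then staying off drug: a departure from the row, yet allowed by Section 5.5. In the Grade 4 row with bilirubin below Grade 4, the position is reversed: the hold binds and the restart is open to judgment.

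**The case against.** The strongest reply is that an investigator reading the protocol as a whole would not be misled. Section 5.2.9 places restart after recovery, and Grade ≤ 1 stands in the bullet just before the restart instructions. The worst-grade reading is natural, and on it the Required Action merely sets the dose level once dosing resumes. Section 5.5 means nobody is compelled to resume, and Section 5.2.10 directs uncertain cases to the medical monitor. Advisory holds also appear elsewhere in the table (pneumonitis Grade ≤ 1, other nonhematological Grade ≥ 3).

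Much of this stands, and it rules out three stronger conclusions that a reader might draw:

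- **That Section 7.3.3 contradicts the table.** It recounts earlier experience with transaminases and says that Grade 3 or 4 elevations can be managed by withholding. That is compatible with an advisory hold. The sequence it describes is not the one the row states, but it sets no opposing rule.
- **That a subject with ongoing Grade ≥ 3 bilirubin must be dosed.** This is one reading of four, and Section 5.5 leaves a way out.
- **That results would not be comparable between sites.** The SAP plans no subject grouping and no formal testing, and it presents exposure, discontinuation and adverse events as by-subject listings.

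The reply does not explain the reversal between adjacent hepatic rows or the required restart, and it relies on inference for both the recovery level and the meaning of the bilirubin grade. Table 5-2 cites the prescribing information, and Section 7.5.2 refers to the investigator's brochure. Neither is available here, so what the sponsor intended cannot be settled.

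**Conclusion.** The point holds as an internal inconsistency in a safety instruction. The Grade 3 hepatic row makes the hold variable and the restart required, gives the restart no explicit recovery condition, and does not define the bilirubin grade. It conflicts with the Grade 4 hepatic row and with Section 5.2.9, sits poorly with the discretion in Section 5.5, and is not aligned with the practice described in Section 7.3.3. The Grade 4 restart line shares the missing recovery condition.

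The reach is limited. The row applies only to events in the Grade 3 range. About 6 subjects were planned and 3 were enrolled (SAP Section 1.3), so at most 3 subjects could be affected. The documents give no rate of Grade 3 hepatic events from which to estimate how many would be. The conclusion assumes that the labels carry the force Section 5.2.10 gives them and that the table's layout has survived text extraction. It should be corrected because it concerns what is binding for safety; no planned analysis changes.

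**What to change.** The sponsor should reconcile the Grade 3 and Grade 4 hepatic rows of Table 5-2 with Sections 5.2.9, 5.2.10, 5.5 and 7.3.3, so that:

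1. the Required and Recommended labels on withholding and resumption are consistent between the two rows and with Section 5.2.9;
2. each row states when its restart instruction applies, and whether the Grade ≤ 1 level governs restart or only monitoring;
3. each row says whether the bilirubin grade is the current or the worst grade;
4. the relation between a required restart and the investigator's discretion to discontinue is stated.

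Which clinical rule is right is for the sponsor to decide. The cost is protocol wording only, with no change to data collection or to the SAP's listings. If treatment has already ended, a short statement in the study report of how any Grade 3 or 4 hepatic event was handled would serve, drawn from the planned adverse event, liver and drug administration listings.
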